Referral pathway initiation. Within seven calendar days of AYA NA-SB completion, the implementation leader will review completed needs assessments and, depending on AYAs' preferences indicated at the end of the needs assessment, will either (a) initiate appropriate referral pathways, or (b) provide a list of recommended referrals to AYAs. For each needs assessment reviewed, they will document these actions on a brief fidelity checklist which timestamps their completion of these tasks, documents the referral pathways selected, and gauges their confidence in selecting appropriate referral pathways (**Appendix B**). This process is expected to take less than 10 minutes/ needs assessment.

Postintervention AYA survey. One month following their completion of the needs assessment, I will engage AYA pilot participants in an online postintervention survey (**Appendix C**) assessing their perceptions of AYA NA-SB's feasibility, acceptability, and appropriateness. In addition to items assessing AYAs' perspectives of the needs assessment itself, this survey will solicit information about the follow-up care AYAs received in response to needs they reported in the needs assessment and whether they felt their needs were met (Aim 2). This survey will administered through RedCAP and will take approximately 15 minutes to complete. AYAs will receive a second \$15 incentive for completing the postintervention survey.

Postintervention provider interview. I will conduct a semi-structured interview with the implementation leader and other participating providers from NCCH after AYA NA-SB has been administered to a minimum of n=15 AYAs. The purpose of this 1-hour interview is to assess provider perceptions of the feasibility, acceptability, and appropriateness of AYA NA-SB and to elicit information about perceived implementation determinants and strategies deployed. Interviews will be recorded and transcribed for analysis. **Appendix D** contains the interview guide.

Activity	Provider Training	Needs assessment administration	Referral pathway initiation	Postintervention AYA survey	Postintervention provider interview
Time	0	+6 weeks	+7 weeks	+10 weeks	+10-15 weeks

Instruments & procedure (Aims 3)

I will conduct annual semi-structured qualitative interviews with AYA providers and program leaders from diverse health systems to proactively address challenges and prepare for future AYA NA-SB scale-up and sustainability.

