	Prevalence of needs by follow demographic/clinical variable	$\operatorname{ss}(?)$		
Services rendered	reported needs	ays initiated in response to AYAs'	Providers	Fidelity Checklist
	needs reported by AYAs	esources rendered in response to	AYAs	Postintervention AYA survey
Care coordination	The delivery of multidisciplinary services to address needs reported by AYAs	AYA's receipt of services/ resources from across disciplines to address reported needs within one month of needs assessment completion	AYAs	Postintervention AYA survey
Needs met	Extent to which services and resources received met reported needs	AYAs' perception of the degree to which their needs were adequately addressed during the study period	AYAs	Postintervention AYA survey

Analytical Plan

Aim1. I will report descriptive

statistics on demographic and clinical variables. I will also calculate descriptive statistics on all quantitative implementation outcomes. Index scores will be generated for each measure by calculating an unweighted average of items within each construct. Further, I will conduct bivariate analyses to assess whether implementation outcomes vary by demographic and clinical variables to ensure that AYA NA-SB is feasible, acceptable, and appropriate across patient characteristics.

Qualitative interview data will be analyzed using template analysis²¹ based on a priori themes (i.e., Proctor's model and CFIR constructs) but allowing for additional emergent themes. A peer and I will independently abstract data from interview transcriptions per Proctor outcomes and CFIR constructs and discuss discrepancies until consensus is reached. When necessary, a third party will be pulled in to resolve discrepant coding.

Aim 2. I will calculate descriptive statistics on AYAs' identified needs, reporting the prevalence of specific needs and needs within specific domains, as well as on services received. I will also calculate descriptive statistics on quantitative service and patient outcomes. I will conduct bivariate analyses to assess whether service and patient outcomes vary by demographic and clinical variables.

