Aim 3. Interview data will be analyzed using template analysis²¹ of interview transcriptions based on a priori themes (i.e., domains of the Dynamic Sustainability Framework) but allowing for additional emergent themes. A peer and I will independently abstract data from interview transcriptions and discuss discrepancies until consensus is reached. When necessary, a third party will be pulled in to resolve discrepant coding.

Human Subjects Protection

Subject Recruitment Methods

Aim 1/2: AYAs will be recruited by the implementation leader who, during routine encounters with AYAs, will provide a brief description of the study objectives and a 1-page recruitment flyer with additional details (**Appendix F**). Additionally, they will receive a fact sheet containing all of the relevant information from the consent form template (**Appendix G**). The implementation leader will distribute the needs assessment link to AYAs interested in participating (via a secure patient portal message), following up with non-responders using Dillman's approach for maximizing survey response rates which includes initial contact, then follow-up with non-responders at 1, 3, and 7 weeks.²²

When recruiting AYAs, implementation leaders will prioritize achieving heterogeneity in terms of cancer type, gender/sex, and race/ethnicity. The implementation leader will not share the identity of AYAs interested in participating, even to members of the study team.

Aim 3: Four interviewees have already been identified: (1) Program Manager, Stanford AYA Cancer Program, (2) AYA Nurse Navigator, University Hospitals, (3) Program Coordinator, Bon Secours St. Francis Cancer Center, and (4) Patient Navigator, Fort Worth AYA Oncology Coalition. With expressed support from Teen Cancer America, an advocacy group that consults with AYA programs around the country, I will identify four additional key contacts (i.e., AYA providers) from diverse health systems. I will email these key contacts information about the study, following Dillman's approach for maximizing response rates which includes initial contact, then follow-up with non-responders at 1, 3, and 7 weeks.²² Key contacts will identify individuals within their institution who are best equipped to participate in these annual interviews.

Informed Consent

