Appendix C: Postintervention AYA survey

Acceptability of Intervention Measure (AIM)

	Completely disagree	Disagree	Neither agree nor disagree	Agree	Completely agree
1. The needs assessment meets my approval.	①	2	3	4	(5)
2. The needs assessment is appealing to me.	①	2	3	4	(5)
3. I like the needs assessment.	①	2	3	4	(5)
4. I welcome the needs assessment.	①	2	3	4	(5)

Intervention Appropriateness Measure (IAM)

	Completely disagree	Disagree	Neither agree nor disagree	Agree	Completely agree
1. The needs assessment seems fitting.	①	2	3	4	(5)
2. The needs assessment seems suitable.	①	2	3	4	(5)
3. The needs assessment seems applicable.	①	2	3	4	(5)
4. The needs assessment seems like a good match.	①	2	3	4	(5)

Feasibility of Intervention Measure (FIM)

	Completely disagree	Disagree	Neither agree nor disagree	Agree	Completely agree
1. The needs assessment seems implementable.	①	2	3	4	(5)
2. The needs assessment seems possible.	①	2	3	4	(5)
3. The needs assessment seems doable.	①	2	3	4	(5)
4. The needs assessment seems easy to use.	①	2	3	4	(5)

Face validity/ content validity

	Completely disagree	Disagree	Neither agree nor disagree	Agree	Completely agree
1. The needs assessment helped me to communicate my needs.	1	2	3	4	(5)
2. The needs assessment was relevant to me.	①	2	3	4	(5)
3. The needs assessment included all needs that I was concerned about.	•	2	3	4	\$

Usability

e successive y					
	Completely disagree	Disagree	Neither agree nor disagree	Agree	Completely agree

1. I think that I would like to complete the needs assessment again.	①	2	3	(4)	(5)
2. I found the needs assessment too complicated.	①	2	3	4	(5)
3. I think the needs assessment was easy to complete.	①	2	3	4	(5)
4. I think I would need help to complete the needs assessment.	①	2	3	4	(5)
5. I felt very confident completing the needs assessment.	1	2	3	4	(5)

Usefulness

	Completely disagree	Disagree	Neither agree nor disagree	Agree	Completely agree
1. The needs assessment provided a helpful way for me to tell my doctors what I need.	①	2	3	4	(5)
2. I did use or would use services and resources offered to me by my doctors based on the needs I checked in the needs assessment.	•	2	3	4	⑤

Care coordination/Needs met

	Yes	No
1. I reported no needs on the needs assessment	① (skip to end)	©
2. I received follow-up care for the needs I reported (e.g., referrals, counseling, other services or resources)	0	② (skip to end)

3. Please indicate the type of follow-up care that you received. (check all that apply)

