(1) communication from my primary oncology team
(2) a phone call or visit from a social worker
(3) a phone call or visit from a nurse navigator
(4) A referral to a specialist (e.g., fertility counselor, nutritionist, physical therapist, etc.)
(5) educational materials
(6) other

	Completely disagree	Disagree	Neither agree nor disagree	Agree	Completely agree
4. The follow-up care I received addressed my needs.	①	2	3	4	(5)

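### Care coordination has a one-month window, but the survey items that measure it have none, so late answers can count later care and overstate the proportion.

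*Combined protocol and SAP*

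**What the plan says.** The Outcome Measure(s) table sets the window for care coordination at "within one month of needs assessment completion" and names the postintervention AYA survey as the data source.

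The section Instruments & procedure (Aims 1, 2) gives the timing of that survey: "One month following their completion of the needs assessment, I will engage AYA pilot participants in an online postintervention survey". The schedule table agrees, with the needs assessment at week 6 and the survey at week 10.

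Three items in the Care coordination/Needs met block of Appendix C matter here:
- Item 2 is yes/no: "I received follow-up care for the needs I reported". A no ends the survey.
- Item 3 is a tick list of six types of care: "Please indicate the type of follow-up care that you received".
- Item 4 is a five-point agreement item: "The follow-up care I received addressed my needs".

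None of the three has a recall period or asks when care was received.

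The neighbouring outcome, Needs met, has a different window. It asks how far AYAs feel that "their needs were adequately addressed during the study period". Services rendered is also taken partly from this survey, and its visible text gives no one-month limit.

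For Aim 2 the Analytical Plan says: "I will also calculate descriptive statistics on quantitative service and patient outcomes". It adds bivariate analyses by demographic and clinical variables and does not mention surveys answered late.

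**The concern.** The definition fixes the follow-up time, and the instrument does not. As written, items 2 and 3 record care received up to the day of answering. For an AYA who answers weeks after the invitation, that period is longer than the definition allows, and nothing in the data would show which care fell inside the month. The fidelity checklist in Appendix B cannot restore the window, because it dates the provider's review and the start of referrals, not the receipt of care.

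Receipt is cumulative: once care has been received, more waiting time cannot undo it. Unlike random error, this error therefore runs in one direction and does not shrink as the sample grows.

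Aim 2 is meant to establish proof of concept, and care coordination is one of its few service outcomes. In the bivariate analyses, if one group tends to answer later than another, its longer exposure time could look like better care coordination. Pilot data will also be reviewed with the Aim 3 interviewees, so an overstated figure could carry into planning for scale-up.

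**Working it through.** **The plan's own interval.** Survey at week 10, needs assessment at week 6: 10 − 6 = 4 weeks, or 28 days. This agrees with the one month in the text. An answer given when the survey arrives covers about the defined window, so on-time answers add no bias of this kind.

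**Definition against items.** The definition has a start (completion of the assessment) and an end (one month). Items 2 and 3 have the start only by implication, through the needs reported, and have no end. The visible text gives no closing date and no late-answer rule. Appendices F to H were not available for this check.

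**Formula.** Let
- p = true proportion meeting the definition at one month;
- L = share of respondents who answer late;
- q = chance that a late respondent who did not meet it at one month comes to meet it before answering.

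Observed proportion = p + L × (1 − p) × q, so bias = L × (1 − p) × q. This takes late and on-time respondents to have the same p, and recall to be complete.

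**Numbers.** The documents give none of p, L or q. The values below are assumptions: p from 0.4 to 0.8, L from 0.2 to 0.6 and q from 0.1 to 0.5, with L = 0 as the reference case.

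| p | L | q | Bias = L × (1 − p) × q | Observed |
|---|---|---|---|---|
| 0.6 | 0 | any | 0 | 60.0% |
| 0.8 | 0.2 | 0.1 | 0.2 × 0.2 × 0.1 = +0.4 points | 80.4% |
| 0.6 | 0.2 | 0.25 | 0.2 × 0.4 × 0.25 = +2.0 points | 62.0% |
| 0.6 | 0.4 | 0.5 | 0.4 × 0.4 × 0.5 = +8.0 points | 68.0% |
| 0.4 | 0.6 | 0.5 | 0.6 × 0.6 × 0.5 = +18.0 points | 58.0% |

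With anyone late, the grid runs from +0.4 to +18.0 points.

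**Scale.** The 95% half-width is 1.96 × √(p(1 − p)/n). At p = 0.6 it is 1.96 × √(0.24/50) = 13.6 points for n = 50 and 1.96 × √(0.24/25) = 19.2 points for n = 25, the two ends of the planned sample, if everyone answers. Most of the grid lies inside the sampling error.

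**The case against.** The strongest reply is that the schedule supplies the window. The survey goes out at one month, so a prompt answer is a one-month answer. Inflation needs both late answers and new care after one month, and the documents give no figure for either. The provider is to act on each assessment within seven days, so care may well be front-loaded, with little left to arrive after the month. Late respondents may also forget care, which would pull the other way. Finally, this is a single-arm pilot with descriptive outcomes and no stated success threshold, so no decision turns on the proportion. All of this stands, and it limits the point to what late answers can do.

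A reader might infer something stronger: that the reminder schedule, "follow-up with non-responders at 1, 3, and 7 weeks", also governs this survey, so that answers arrive 4 + 1 = 5, 4 + 3 = 7 or 4 + 7 = 11 weeks after the assessment. If half had care by day 30 and receipt continued at a constant rate, the items would then capture 1 − 0.5^(51/30) = 69% at day 51 and 1 − 0.5^(79/30) = 84% at day 79. With 30% answering that late, the result would be 0.7 × 0.5 + 0.3 × 0.69 = 56% or 0.7 × 0.5 + 0.3 × 0.84 = 60%, against a true 50%. The documents do not support this reading. Subject Recruitment Methods states those reminders for the needs assessment link and the Aim 3 contacts, not for the postintervention survey. The constant rate is an assumption. The sum also counts any single service, whereas the outcome requires services from across disciplines.

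What the reply does not answer is that the plan sets no closing date or late-answer rule, and nothing in the items would allow late care to be removed afterwards.

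**Conclusion.** The point holds as a mismatch between a definition and its instrument. Late answers can overstate the one-month proportion, and the plan has no means to prevent or detect it. The documents do not show that the outcome is inflated. The bias is zero if everyone answers on time and +0.4 to +18.0 points over the assumed grid, on the conditions of equal p in late and on-time respondents and complete recall. It affects a reported proportion and its subgroup comparisons, not a test or a decision rule. It merits correction because the change is small and the information cannot be recovered once the surveys are in.

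**What to change.** - **Items 2 and 3:** leave them open, so that Services rendered is unaffected and an AYA whose care came later is not sent to the end of the survey. For each type of care ticked in item 3, add a tick for whether it was received within one month of the needs assessment or only later. Show the assessment date in the question, piped from REDCap.
- **Care coordination:** count only care ticked as within one month. Report later care separately.
- **Item 4:** leave it unchanged. Needs met is defined over the study period, and a one-month window there would create a new mismatch.
- **Analysis:** use the REDCap timestamps to report days from assessment to survey. Add a sensitivity analysis limited to surveys answered within a window fixed before data collection. This does not depend on recall of dates, but prompt respondents may differ from late ones, so it should support the main figure and not replace it.

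The cost is one extra tick per type of care reported, at most six, and a piped date. The reported proportion may come out slightly lower.

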Aim 1/2: I will pilot AYA NA-SB in the North Carolina Cancer Hospital (NCCH). NCCH is a public, National Cancer Institute-designated Comprehensive Cancer Center located in central North Carolina, in a relatively metropolitan area. At NCCH, around 450 individuals ages 15-30 are diagnosed each year. About one third of these patients are treated in pediatric oncology and the remainder in adult oncology. NCCH's AYA program was established in 2015 with funding from a local nonprofit organization, the BeLoud Sophie Foundation. This funding was initially allocated towards hiring one fulltime employee (a social worker/program director) to provide AYA-specific care at NCCH. Since 2015, the program has evolved, hiring new AYA-specific staff members (e.g., nurse practitioner, fertility counselor) and expanding program activities and reach.

Aim 3: I will conduct interviews with providers and program leaders from AYA programs around the country.

Subjects selection criteria

• Inclusion Criteria

Aim 1/2: AYAs with cancer ages 18 through 39 currently in treatment at NCCH Aim 3: AYA providers and program leaders from around the country

• Exclusion Criteria

No exclusion criteria

• Sample Size

- Aim 1/2
 - \circ N=25-50 AYAs
 - o N=25/arm has been proposed as the minimum threshold of sample size for aims related to instrumentation. ¹⁸ Given that this is a single-arm pilot study, we have determined that a sample size between 25 and 50 is appropriate.
- Aim 3
 - N=8 AYA providers/ program leaders. Interviewees will be purposefully sampled such that
 they represent a range of health systems. As such, a sample size of 8 is expected to yield
 adequate data to meet the objectives of Aim 3.

Interventions and Interactions

Intervention (Aims 1, 2)

The intervention, AYA NA-SB, includes three components: (1) a needs assessment, (2) a map of referral pathways, and (3) implementation guidance (**Appendix A**).

Needs assessment. The needs assessment portion of AYA NA-SB is a 57-item PROM which includes nine domains: (1) information, (2) cancer care team, (3) physical health, (4) emotional health, (5) sexual and reproductive health, (6) health behaviors and wellness, (7) work and education, (8) peer support and programming, and (9) finances and everyday needs.

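### Do the ten survey items on face/content validity, usability and usefulness need their own outcome row and stated analysis?

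*Combined protocol and SAP*

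**What the plan says.** The Sample Size section gives one cited basis for Aims 1 and 2: "N=25/arm has been proposed as the minimum threshold of sample size for aims related to instrumentation". It then concludes: "Given that this is a single-arm pilot study, we have determined that a sample size between 25 and 50 is appropriate". It does not define instrumentation or say which items or outcomes it means.

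The description of the postintervention AYA survey, under Instruments & procedure (Aims 1, 2), says the survey is for "assessing their perceptions of AYA NA-SB's feasibility, acceptability, and appropriateness". The next sentence speaks in general terms of items on how AYAs view the needs assessment, and of items on follow-up care and needs met.

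The Outcome Measures table lists feasibility (FIM), acceptability (AIM), appropriateness (IAM), fidelity, determinants and strategies under Aim 1. Under Aim 2 it lists AYA needs, services rendered, care coordination and needs met.

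The Analytical Plan for Aim 1 states "I will also calculate descriptive statistics on all quantitative implementation outcomes". It scores each measure as an unweighted mean of its items and adds bivariate comparisons by patient characteristics.

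Appendix C contains three further five-point blocks. Examples are "The needs assessment included all needs that I was concerned about" (face/content validity), "I found the needs assessment too complicated" and "I think I would need help to complete the needs assessment" (usability items 2 and 4), and "The needs assessment provided a helpful way for me to tell my doctors what I need" (usefulness).

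**The concern.** Three things together make this look like a defect. First, more than a third of the survey has no declared outcome, so which of these items are reported, and whether singly or as an index, would be settled after the data are in. Second, the sample size appeals to instrumentation, and the blocks headed validity, usability and usefulness are the ones most obviously about the instrument. The plan can therefore seem to justify its size by an analysis it does not contain. Third, if the unweighted-mean rule were carried over to usability, two of the five items point the other way and no reverse scoring is mentioned. At stake would be selective reporting of the instrument's ratings and a usability score squeezed towards the middle of its scale.

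**Working it through.** **Sample size.** The figure of 25 to 50 cannot be reproduced. The documents give no error rate, power, effect size, standard deviation, target precision or dropout, only a cited threshold. Nothing below depends on recomputing it.

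**Item count (Appendix C against the Outcome Measures table).**

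| Block | Items | Outcome row |
|---|---|---|
| AIM | 4 | Acceptability |
| IAM | 4 | Appropriateness |
| FIM | 4 | Feasibility |
| Face/content validity | 3 | none |
| Usability | 5 | none |
| Usefulness | 2 | none |
| Care coordination/Needs met | 4 | Services rendered, care coordination, needs met |

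Total: 4 + 4 + 4 + 3 + 5 + 2 + 4 = 26. Without a row: 3 + 5 + 2 = 10, and 10/26 = 38.5%. With a row: 26 − 10 = 16. Some cells of the table are broken by text extraction, but the variable names are legible and there is no sign of a lost row.

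**Are the listed outcomes scored soundly?** The twelve AIM, IAM and FIM items are all worded so that agreement is favourable, on a common 1–5 scale. An unweighted mean is therefore a valid index for each, and no listed measure needs recoding.

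**Usability, if an index were formed.** Take a respondent who consistently holds a view at level L (1 = worst, 5 = best). Items 1, 3 and 5 are answered L. Items 2 and 4, being negative, are answered 6 − L.

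- Without recoding: [3L + 2(6 − L)]/5 = (L + 12)/5 = 2.4 + 0.2L. L = 1 gives 2.6 and L = 5 gives 3.4, a span of 0.8.
- With items 2 and 4 recoded as 6 minus the response: (3L + 2L)/5 = L. The span is 1.0 to 5.0, or 4.0.

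An unrecoded mean would thus keep one fifth of the range (0.8/4.0). This depends on two steps the plan does not announce: forming a usability index, and leaving the items unreversed. Item-by-item reporting needs no recoding.

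**The link to sample size.** Every one of the twelve AIM, IAM and FIM items in Appendix C takes the needs assessment as its subject, including a feasibility item on ease of use. These are respondent ratings of the instrument, and they have rows, a scoring rule, descriptive summaries and bivariate comparisons. A rationale about instrumentation can attach to them without the ten extra items.

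**Place of the ten items in the study.** The Background reports that usability testing was part of development and that the result was judged highly usable and useful. It names implementation and efficacy as what is still untested, and Aims 1 and 2 follow that division. Items on usability and usefulness with no outcome row are most naturally read as supplementary.

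**The case for a change.** The strongest case for a change is that usability and usefulness are not incidental. The Background expects those very qualities to carry the intervention into practice, and these items are the pilot's direct patient ratings of them. The general sentence about AYAs' views of the needs assessment shows that the items are collected, not how they will be summarised. If the averaging rule is taken to apply to every construct in the survey, it gives a poor usability score; if it is not, there is no rule. Either reading could be settled by one table row and two or three sentences, with no new data.

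The omission stands, and so does the warning about an unreversed usability mean. Much less stands of the consequence. In context the averaging rule follows the sentence on implementation outcomes, which the table limits to named measures, so the plan does not direct anyone to average the usability block. The contrary wording of items 2 and 4 is plain on the page, and reversing them is routine. Freedom to choose between items and an index matters most where a result can turn on it. This single-arm pilot sets no success threshold and no confirmatory test that these ten items could influence. The cited threshold is not shown to be wrong, and to name the ten items as its purpose would supply a rationale the protocol does not give.

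**Conclusion.** No change to the plan is needed. Ten of 26 survey questions (38%) have no outcome row or named analysis, but none of the listed Aim 1 or Aim 2 outcomes is mis-scored or left without a summary because of it. Neither the sample size nor the data collected would differ. The sensible handling is what an analyst would do anyway: treat the ten items as supplementary, describe them one by one, and reverse usability items 2 and 4 before any average is taken. The compression to 2.6–3.4 is arithmetically correct but arises only if an unannounced index is built carelessly. This conclusion assumes that the ten items stay descriptive and are not later promoted to a headline result or a go/no-go criterion, neither of which the documents suggest.

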To facilitate a systematic and patient-centered approach to delivering services and resources to address the unmet needs of adolescents and young adults (AYAs) with cancer, we developed in preliminary studies the AYA Needs Assessment & Service Bridge (AYA NA-SB). AYA NA-SB includes (1) a holistic PROM assessing AYAs' physical, psychosocial and practical needs and (2) a collection of referral pathways for connecting AYAs to services and resources based on the needs they report (see **Appendix A**). To optimize AYA NA-SB's usability (i.e., ease of use) and usefulness (i.e., link to services), promote cancer programs' receptivity to AYA NA-SB implementation, and anticipate implementation strategies needed to facilitate AYA NA-SB's successful implementation and sustainment, we conducted usability testing, an ethnographic user and contextual analysis, and iterative prototyping workshops with a multidisciplinary design team.

Our development process culminated in an intervention with high usability and usefulness, characteristics we expect to promote AYA NA-SB's successful implementation and achievement of desired outcomes; however, AYA NA-SB's implementation and efficacy remain untested. Thus, through this study, we will evaluate AYA NA-SB's implementation and establish proof-of-concept. To avoid creating a tool that is only applicable to its high-resource testing environment, I will also plan for AYA NA-SB's potential scale-up across diverse health systems serving AYAs with cancer.

Objectives

Aim 1. Assess the implementation of AYA NA-SB. I will pilot AYA NA-SB in the North Carolina Cancer Hospital (NCCH), with a primary focus on implementation outcomes.

Aim 2. Establish proof-of-concept for AYA NA-SB. I will use pilot data to generate preliminary evidence on the extent to which AYA NA-SB addresses AYAs' reported needs.

Aim 3. Plan for AYA NA-SB's scalability and sustainability in diverse health systems. I will conduct annual 60-minute semi-structured qualitative interviews with AYA providers and program leaders from approximately 8 health systems to proactively address challenges and prepare for future AYA NA-SB scale-up and sustainability.

Methods and Measures

Design

- Aim 1/2: Single-arm feasibility pilot
- Aim 3: qualitative interviews

Setting

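### Does the plan's item-averaging rule mis-score the Usability block, in which two of the five items run the other way?

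*Combined protocol and SAP*

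**What the plan says.** The Analytical Plan for Aim 1 promises descriptive statistics on demographic and clinical variables. It continues: "I will also calculate descriptive statistics on all quantitative implementation outcomes". The scoring rule comes next: "Index scores will be generated for each measure by calculating an unweighted average of items within each construct". The sentence after that announces bivariate analyses of the implementation outcomes by patient characteristics, to check that the intervention is "feasible, acceptable, and appropriate across patient characteristics".

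The table under Outcome Measure(s) lists the Aim 1 implementation measures. Those taken from the patient survey are the Feasibility of Intervention Measure (FIM), the Acceptability of Intervention Measure (AIM) and the Intervention Appropriateness Measure (IAM). The description of the postintervention AYA survey, under the Aims 1 and 2 procedures, names the same three perception constructs.

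Appendix C collects more than these. After AIM, IAM and FIM come blocks on face and content validity, Usability and Usefulness. The Usability block has five items, each coded from 1 (completely disagree) to 5 (completely agree). Items 1, 3 and 5 are favourable, for example "I think that I would like to complete the needs assessment again" and "I think the needs assessment was easy to complete". Items 2 and 4 are unfavourable: "I found the needs assessment too complicated" and "I think I would need help to complete the needs assessment". The available text neither states nor rules out reversal of these two items.

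**The concern.** The rule speaks of each measure and each construct. In Appendix C the Usability block looks just like the three listed scales: a headed set of agreement items on the same five-point scale. A reader who takes the rule at face value could average all five responses as coded, and agreement that the tool was too complicated would then raise the usability score.

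The reported level would suffer first. Good and poor usability would both come out near the neutral value of 3, which would sit oddly with the Background's statement that development produced "an intervention with high usability and usefulness". If such an index were then compared between patient groups, in a pilot of only 25 to 50 patients, part of any real difference would be lost. The pilot data are also to be shown to the Aim 3 interviewees, so a misleading score could travel further.

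**Working it through.** The plan states no figure for this point, so there is none to reproduce. The check has two parts: what raw averaging would do, and whether the plan calls for it.

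**Inputs.** The five Usability items, their direction and the 1 to 5 coding come from Appendix C. The averaging rule comes from the Analytical Plan, Aim 1. Reversal means replacing a response by 6 minus that response.

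**Level.** Take a respondent whose view of usability is consistent at level x: x on items 1, 3 and 5, and 6 − x on items 2 and 4.

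- Raw mean: (3x + 2(6 − x))/5 = (x + 12)/5.
- Mean with items 2 and 4 reversed: (3x + 2x)/5 = x.

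| Responses to items 1–5 | Raw mean | Mean after reversal |
|---|---|---|
| 5,1,5,1,5 (best) | 17/5 = 3.4 | 5.0 |
| 4,2,4,2,4 | 16/5 = 3.2 | 4.0 |
| 3,3,3,3,3 | 15/5 = 3.0 | 3.0 |
| 2,4,2,4,2 | 14/5 = 2.8 | 2.0 |
| 1,5,1,5,1 (worst) | 13/5 = 2.6 | 1.0 |
| 5,5,5,5,5 | 25/5 = 5.0 | 17/5 = 3.4 |

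The span from consistently worst to consistently best shrinks from 4.0 points to 0.8.

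**Discrimination.** The documents give no inter-item correlation, so assume a common correlation rho between items once they are aligned. The raw mean keeps (3 − 2)/5 = one fifth of the signal but the same item noise. The standardised group difference, raw relative to reversed, is then

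sqrt([rho + (1 − rho)/5] / [rho + 5(1 − rho)]).

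- rho = 0.3: sqrt(0.44/3.8) = 0.34
- rho = 0.5: sqrt(0.60/3.0) = 0.45
- rho = 0.7: sqrt(0.76/2.2) = 0.59
- rho = 1.0: sqrt(1/1) = 1.00

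Raw averaging of this block would therefore be a poor score under any realistic correlation.

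**Does the plan call for it?** Set the places side by side.

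- The sentence before the rule limits the subject to quantitative implementation outcomes. The sentence after it names feasibility, acceptability and appropriateness.
- In the outcome table, the patient-survey measures for Aim 1 are FIM, AIM and IAM, one for each of those constructs. Usability has no row under Aim 1 or Aim 2.
- The Aim 1 bivariate analyses cover implementation outcomes, and the Aim 2 ones cover service and patient outcomes. Usability is listed as neither, so no Usability comparison is planned.
- FIM, AIM and IAM have four items each. All 3 × 4 = 12 are favourable when agreed with, so their unweighted means run from 4/4 = 1.0 to 20/4 = 5.0 in the right direction.

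Read with its neighbouring sentences and the outcome table, the rule covers three scales for which it is correct.

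**The case for a change.** The strongest reply is that the rule's wording is general and the layout of Appendix C invites its use on Usability. If the rule does not reach that block, five items are collected with no stated analysis, although the Background relies on high usability. One added sentence would settle either reading at almost no cost.

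Some of this stands. Items 2 and 4 do run opposite to the others, the available text mentions no reversal, and no scoring is given for the block. The same silence covers the face and content validity and the Usefulness blocks, though all of their items are positively worded. A clarifying sentence would do no harm.

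It does not amount to an error in the plan. Aligning item direction before averaging is routine, and anyone who sees the complexity item beside the ease-of-completion item will notice the need. The loss of discrimination belongs to a comparison that the plan does not include, and its size rests on an assumed correlation. The all-5 pattern in the table comes from a respondent who agrees completely that the tool was both too complicated and easy, and its reversed score of 3.4 is hard to interpret as well. The Background's usability statement reports earlier development work, and no section sets out to test it with an index from this survey.

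**Conclusion.** The observation about item direction is correct, but no change to the plan follows. For every listed multi-item survey scale the rule gives the right score. The compression to between 2.6 and 3.4 would occur only if an index were built for an unlisted block and its items were left unaligned. The plan asks for neither. Sample size, listed outcomes and planned comparisons are all unaffected.

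This is a gap that analysts fill sensibly: report the five Usability items one by one or, if an index is wanted, take 6 minus the response on items 2 and 4 before averaging. Either can be done from the recorded responses after data collection.

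The conclusion rests on two assumptions: that the outcome table defines what the Aim 1 rule covers, and that the appendix pages not available for this review do not define a Usability index.
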